4. GENERAL ANALYSIS AND REPORTING CONVENTIONS

The following is a list of general analysis and reporting conventions to be applied for this study:

- Categorical variables will be summarized using counts (n) and percents (%) and will be presented in the form n (%).
- Moment statistics including mean will be reported at 1 more significant digit than the precision of the original data. The standard deviation will be reported at 2 more significant digits than the precision of the original data. The level of precision may be modified on specific displays based on clinical judgement.
- Order statistics including median, min, and max will be reported to the same level of precision as the original observations. If any values are calculated to have more significant digits, then the value should be rounded so that it is the same level of precision as the original data.
- Following SAS default rules, the median will be reported as the average of the two middle numbers if the dataset contains an even number of observations.
- Test statistics including t and z test statistics will be reported to two decimal places.
- P-values will be reported to 3 decimal places if greater than 0.001; if less than 0.001, then they will be reported as ‘<0.001’. P-values and significant levels will be reported as 0.05 rather than .05. A p-value will be reported as “1.000” only if it is exactly 1.000 without rounding. A p-value will be reported as “0.000” only if it is exactly 0.000 without rounding.
- No preliminary rounding should be performed; rounding should only occur after analysis. To round, consider the digit to the right of last significant digit; if <5 then round down, and if ≥ 5 then round up.
- In general, listings will be displayed by treatment arm and subject and will be sorted in the order that columns are displayed, starting with the first column on the left.
- All analyses will be performed using the SAS System version 9.4 or higher.

5. ANALYSIS SAMPLES

Analysis samples for ACV01 for each study stage (Stage 1, Stage 2) and age group (Adult, Pediatric) will be defined as follows:

- **Vaccinated population:** will be defined as all participants who are randomized or allocated and receive study vaccine in the study. For all endpoints, participants will be evaluated by the actual vaccine received. In Cohorts A and B, participants will be analyzed in subgroups defined by randomized assignment to continue or withhold IS medications in the primary analysis.
- **Per protocol populations:** will be defined as the subgroup of participants in the vaccinated population who adhere to the treatment plan for IS medications defined in Section 7.1.1 Protocol-mandated Medications and have no major protocol deviations or ineligible entry criteria that would impact the vaccine response assessment at Week 4.
- **Safety population:** will be defined as all participants who initiate the treatment plan for IS medications or receive an additional dose of vaccine.

6. STUDY SUBJECTS

6.1. Disposition of Subjects

The disposition of participants will be summarized in tables and listed for each study stage (Stage 1, Stage 2) and age group (Adult, Pediatric). A CONSORT diagram outlining the flow of participants in the study will also be created. The numbers and percentages of participants randomized/allocated, in each analysis sample, and receiving vaccine, as well as reasons for early termination from the study, will be presented. For participants who were randomized/allocated but did not receive an additional dose of vaccine, the reasons for not receiving vaccine will also be presented. For Stage 2 of the study, the numbers and percentages of participants who are newly recruited vs. rollovers from Stage 1 will be summarized. Study disposition will also be summarized by site.

6.2. Demographic and Other Baseline Characteristics

Summary descriptive statistics for baseline and demographic characteristics will be reported for all analysis samples by study arm. Characteristics to be summarized include:

- Age, race, ethnicity, sex, body weight at screening, height
- Disease type and duration
- Roche Elecsys® Anti-SARS-CoV-2 S result at screening; both as a continuous variable and categorical: negative (≤ 0.79 U/mL) vs. positive (> 0.79 U/mL); additionally, categorized as ≤ 0.79 U/mL, > 0.79 U/mL through 50 U/mL, > 50 U/mL through 200 U/mL, > 200 U/mL
- History of prior SARS-CoV-2 infection at Screening
- Time (in weeks) from previous vaccine series
- Additional IS medications
- Steroid dose
- For Stage 2: previous vaccine series
- Medication dose for or Cohort A: MMF or MPA and Cohort B: MTX
- For Cohort C and Cohort F: B cell depletion therapy:
 - Type of B cell depletion therapy
 - Time (in weeks) from last dose of b cell depletion therapy to vaccine.
 - CD19+ B cells

6.3. Prior and Concomitant Medications

Medications will be coded according to the World Health Organization (WHO) Drug Dictionary: WHO-Drug Global v2021-March. Medications will be reported on both the Immunosuppressive Medication and Concomitant Medications case report forms (CRFs).

The number and percentage of participants receiving IS medications will be presented overall and by medication class. Immunosuppressive medications will also be summarized by disease type. When reporting the number of subjects receiving the medication, a subject will only be counted once if they ever received the medication within the medication class. Percentages will be based on the number of subjects in the analysis population. Medications will also be listed.

The numbers and percentages of participants receiving the following concomitant medications will be presented overall and by medication class:

- SARS-CoV-2 vaccines or live vaccines (of any kind) administered outside of the study.
- Monoclonal antibodies administered for (a) pre-exposure prevention of COVID-19, (b) post-exposure prevention of COVID-19, or (c) treatment of COVID-19 infection.

6.4. Medical History

Analysis details will be provided in subsequent versions of the SAP.

7. STUDY OPERATIONS

7.1. Protocol Deviations

Protocol deviations will be listed by site with information such as date of deviation, category, description and reason for deviation, and corrective action taken. Protocol deviations will be summarized overall and by site in tabular format by type of deviation.

7.2. Randomization and Allocation

When employed in any population, randomization will be accomplished through a password-protected, web-based randomization system. The investigators, clinic personnel, and participants will not be blinded to randomized treatment assignments. Statistical and project staff at the Statistical and Clinical Coordinating Center (SACCC) and the DAIT Medical Monitor and Project Manager will be unblinded to individual treatment assignments as well. Laboratories performing assays for this protocol will be blinded to the identity and group assignment of biological materials to be studied.

7.2.1. Adult Stage 1

Participants who sign the informed consent form and meet all eligibility criteria for Stage 1 will be assigned to cohorts defined by IS medication and by the initial COVID-19 vaccine regimen received. Participants in Cohort C will be allocated to continuing to take their prescribed IS medications throughout the trial. Participants in Cohorts A and B will be randomized in a balanced fashion (1:1), within the cohorts defined by IS medication and initial COVID-19 vaccine regimen, to one of the available IS medication treatment plans (continue cohort-defining IS vs. withhold cohort-defining IS). Randomization will be performed using a permuted block design stratified by disease type.

A total of 60 participants with a Roche Elecsys® Anti-SARS-CoV-2 S result ≤ 200 U/mL will be randomized or allocated to each arm. In each arm, the number of participants with Roche Elecsys® Anti-SARS-CoV-2 S results ≤ 50 U/mL will be capped at 40 participants, and the number of participants with Roche Elecsys® Anti-SARS-CoV-2 S results >50 U/mL and ≤ 200 U/mL will be capped at 40 participants.

7.2.2. Adult Stage 2

Participants who have signed the informed consent form and meet all eligibility criteria for Stage 2 will be allocated to cohorts defined by IS medication and by the initial COVID-19 vaccine regimen received. Participants who received either the Moderna COVID-19 Vaccine or Pfizer-BioNTech COVID-19 Vaccine will be allocated to the Stage 2 Arm that corresponds to their choice of either the Janssen vector-based COVID-19 vaccine or the other mRNA COVID-19 vaccine. Participants who received the Janssen COVID-19 Vaccine will be allocated to the Stage 2 Arm that corresponds to the Moderna COVID-19 Vaccine. Participants in Cohort D will withhold their MMF/MPA, participants in Cohort E will withhold their MTX, and any participants in Cohort F (B cell depletion therapy) who are also taking MMF/MPA or MTX will withhold these medications. No randomization will be employed.

A total of 60 participants with a Roche Elecsys® Anti-SARS-CoV-2 S result ≤ 200 U/mL will be allocated to each arm. In each arm, the number of participants with Roche Elecsys® Anti-SARS-CoV-2 S results ≤ 50 U/mL will be capped at 40 participants, and the number of participants with Roche Elecsys® Anti-SARS-CoV-2 S results > 50 U/mL and ≤ 200 U/mL will be capped at 40 participants.

7.2.3. Pediatric Population

Participants and their legal guardian(s) who sign the consent and assent forms, as appropriate to age, and meet all eligibility criteria for the pediatric portion of the trial will be assigned to cohorts defined by IS medication and by the initial COVID-19 vaccine regimen received. Participants in Cohort C will be allocated to continuing to take their prescribed IS medications throughout the trial. Participants in Cohorts A and B will be randomized in a balanced fashion (1:1), within the cohorts defined by IS medication and initial COVID-19 vaccine regimen, to one of the available IS medication treatment plans (continue IS vs. withhold IS). Randomization will be performed using a permuted block design stratified by disease type.

A total of 60 participants with a Roche Elecsys® Anti-SARS-CoV-2 S result ≤ 200 U/mL will be randomized or allocated to each arm. In each arm, the number of participants with Roche Elecsys® Anti-SARS-CoV-2 S results ≤ 50 U/mL will be capped at 40 participants, and the number of participants with Roche Elecsys® Anti-SARS-CoV-2 S results > 50 U/mL and ≤ 200 U/mL will be capped at 40 participants.

7.3. Measures of Treatment Compliance

The number of participants who receive study vaccine will be summarized by arm.

In study arms that withhold IS medications around the time of vaccination, the total number of days, the number of days prior to vaccine, and the number of days post-vaccine that IS medications are withheld will be summarized.

8. ENDPOINT EVALUATION

8.1. Overview of Efficacy Analysis Methods

8.1.1. Multicenter Studies

Study participants will be recruited from 15-20 study sites for each of the adult and pediatric groups. Study data will be analyzed as a whole, and no formal accommodation for site-to-site variation will be made.

8.1.2. Assessment Time Windows

Additional details will be provided in subsequent versions of the SAP.

8.1.3. Timing of Analyses

The primary analysis will be evaluated independently within each arm (defined by age, cohort, vaccine, and IS treatment plan) in the vaccinated population, and will be conducted overall, in all participants with a Roche Elecsys® Anti-SARS-CoV-2 S result ≤ 200 U/mL at the Screening visit, and in the subgroup of participants with a Roche Elecsys® Anti-SARS-CoV-2 S result ≤ 50 U/mL at the Screening visit. Each analysis will occur after the evaluable participants assigned to that arm have completed the Week 4 study visit or are withdrawn from the study.

8.1.4. Multiple Comparisons/Multiplicity

The primary analysis will be evaluated independently within each arm, and p-values will not be adjusted for multiple comparisons.

All secondary analyses will be conducted in an exploratory fashion, with any p-values and confidence intervals presented as descriptive statistics with no adjustments for multiple comparisons.

8.2. Primary Endpoint

The primary endpoint of a protective antibody response will be the proportion of participants who reach the laboratory-defined threshold for the NIAID-VRC MSD 3 plex (Wu-1 full-length spike, RBD, and N proteins) assay at Week 4. The Wu-1 full-length spike protein will be used in determining a protective antibody response in the primary analysis; the RBD protein will be used in secondary analyses of antibody response; and N proteins will be used in supportive analyses as evidence of COVID infection.

8.2.1. Computation of the Primary Endpoint

The proportion of participants who reach the laboratory-defined threshold for the NIAID-VRC MSD 3 plex assay at Week 4 will be summarized by arm overall, in all participants with a Roche Elecsys® Anti-SARS-CoV-2 S result ≤ 200 U/mL at the Screening visit, and in the subgroup of participants with a Roche Elecsys® Anti-SARS-CoV-2 S result ≤ 50 U/mL at the Screening visit.

For concentrations that are below the Lower Limit of Detection (LLOD), numeric values equivalent to LLOD/2 are assigned before and for all descriptive reporting. Concentrations that are above the Upper Limit of Quantification are reported without adjustments.

Participants with missing Week 4 anti-COVID-19 antibody response data with a documented COVID infection prior to Week 4 will be considered as not having a protective antibody response. All other participants missing Week 4 anti-COVID-19 antibody response data will be considered to be missing-completely-at-random (MCAR).

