1.2 Clinical Trial Design and Rationale

1.2.1 Initial Trial Design - Additional Homologous Vaccine Dose

This clinical trial was initially designed to assess antibody responses to an additional homologous COVID-19 vaccine dose and identify methods for improving COVID-19 vaccine responses in patients with 1 of 5 autoimmune diseases. The diseases included in the trial (SLE, RA, MS, pemphigus, and systemic sclerosis [SSc]) were chosen based on prevalence rates, use of background medications of interest, and/or availability of pre-existing cohorts among the current Autoimmune Centers of Excellence (ACE) associated institutions. The medications of interest, MMF/ mycophenolic acid (MPA), MTX, and B cell depleting drugs, are used commonly in these patient populations and have been associated with poor vaccine response as described above. Only autoimmune disease patients with a negative or suboptimal serologic response to the initial COVID-19 vaccine regimen will be included in this clinical trial. Using the Roche Elecsys anti-SARS-CoV-2 S enzyme immunoassay, Ruddy et al [17] demonstrated that while many patients with autoimmune diseases have apparently robust antibody to COVID-19 vaccines (median response >250 U/ml) that some, particularly in that study those treated with mycophenolate and B cell depletion, have poor responses (8 U/ml and <0.4 U/ml, respectively).

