13.4.4 Analyses of Secondary and Other Endpoint(s)

For Stage 1, the multivariable logistic and linear regression models defined in Section 13.4.3 Supportive Analyses of the Primary Endpoint above will be used to compare response to additional homologous doses of COVID-19 vaccine for a variety of subgroups. Appropriate contrasts will be defined to compare vaccine response for the following:

- Continuing versus withholding IS medications will be compared within cohort (cohorts A and B only) and within and across type of vaccine.
- The types of additional vaccine dose administered will be compared within cohorts and across cohorts, and within and across IS treatment plan groups.
- Type of IS medications will be compared within and across each type of vaccine.
- Age groups and type of disease will be compared within and across each type of vaccine.
- Corticosteroid dose at baseline will be added as a covariate to the model to assess impact on vaccine response.
- Immune response to the initial COVID-19 vaccine regimen will be assessed within and across each type of vaccine.
- Additional covariates for disease activity, co-morbid illness, age, and sex may be added to assess whether the clinical parameters are associated with response to additional vaccine dose.

Data for the Moderna COVID-19 Vaccine and Pfizer-BioNTech COVID-19 Vaccine may be combined in the comparisons above to assess the effect of mRNA vaccines together.

The incidence of seroconversion following additional vaccine doses of COVID-19 vaccine will be evaluated in the subgroups of participants that are anti-COVID-19 antibody negative at baseline using separately, (a) NIAID-VRC MSD 3 plex (Wu-1 full-length spike, RBD, and N proteins) assay with thresholds <1204.7 , 517.9 , and 9779.6 AU/mL, respectively, and (b) the Roche Elecsys® Anti-SARS-CoV-2 S electrochemiluminescence immunoassay with a threshold <0.80 U/mL. The proportions who seroconvert within and across arms will be summarized using 95% Clopper-Pearson confidence intervals, and comparisons will use a two-sample Binomial exact test with nominal two-sided alpha = 0.05.

For the subgroups of participants that are anti-COVID-19 antibody positive at baseline using separately, (a) the NIAID-VRC MSD 3 plex (Wu-1 full-length spike, RBD, and N proteins) assay, and (b) the Roche Elecsys® Anti-SARS-CoV-2 S electrochemiluminescence immunoassay with a threshold ≥ 0.80 U/mL. Fold improvement for each assay will be defined as:

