13.7 Sample Size Considerations

Early reports show that a significant number of individuals taking IS medications respond poorly or not at all to COVID-19 vaccination. Ruddy et al. reported 26% of chronic inflammatory rheumatic disease patients had undetectable SARS-CoV-2 antibody response after their first mRNA vaccine dose, but many seroconverted with the second dose such that only 6% had persistent undetectable SARS-CoV-2 RBD antibodies [16]. However, those taking MMF or rituximab were at much higher risk of not mounting a detectable antibody response (89% and 67%, respectively)[17]. Another report has demonstrated diminished overall serologic response in adults with chronic inflammatory diseases, particularly in those treated with B-cell depletion or antimetabolites including MTX, with a 50-fold and 3-fold reduction in post-vaccine antibody titers relative to immunocompetent controls[80].

Based on the emerging evidence in individuals taking IS medications, an ineffective rate of achieving a protective immune response after the additional vaccine dose was defined to be less than or equal to 0.25 (null hypothesis). The study is powered to reject the null hypothesis in each arm when the true response rate is 0.5 or greater as preliminary evidence the additional vaccine dose is effective in specific study population.

The proportion of participants in each arm (cohort, additional vaccine dose, and IS treatment plan group) to receive an additional vaccine dose and achieve a protective antibody response at Week 4 will be evaluated using a one-sided exact test with alpha = 0.05 to test against a null hypothesis that the true response rate is ≤ 0.25 . A sample size of 33 evaluable participants achieves at least 90% power to reject null hypothesis when the true response rate is 0.5 or greater.

Secondary analyses will compare the rate of achieving a protective immune response across arms using the multivariable logistic regression model. For comparisons of single arms, 33 evaluable participants per arm will provide 80% power to detect an odds ratio of 4.2 when the null hypothesis is true in one arm (improvement from 0.25 to 0.584). For comparisons that combine arms, pooling 3 arms (e.g., type of additional vaccine dose) will provide 80% power to detect an odds ratio of 2.3 (improvement to 0.394).

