8.2.4. Secondary Analyses of the Primary Endpoint

Descriptive statistics will be used to summarize antibody response to the additional homologous vaccine dose on a continuous scale, including median, minimum, and maximum, interquartile range, geometric mean, CV of the geometric mean, and 95% confidence intervals. Summary statistics, including 25th percentile, mean, median, and 75th percentile, will be plotted for each visit by treatment arm. Geometric mean and CV of the geometric mean will be computed as follows:

$$\text{Geometric mean} = \exp(\text{mean on } \log_e \text{ scale}).$$

$$\% \text{CV geometric mean} = \sqrt{\exp((SD \text{ on } \log_e \text{ scale})^2) - 1} \times 100$$

Primary and secondary analyses will be repeated for the RBD proteins to summarize antibody response to the additional homologous vaccine dose on a continuous scale. Supportive analyses will use descriptive statistics to summarize N protein levels as evidence of COVID infection.

In the final analysis, supportive analyses will also use a multivariable regression model on the entire vaccinated population in order to estimate the rates of vaccine response within and across arms (age group, cohort, vaccine, and IS treatment plan group) using the logistic link function, and including baseline covariates for disease type (SLE, RA, MS, SSc, and pemphigus in adults

and JIA, pediatric SLE, JDM, and POMS in pediatrics) and immune response to the initial COVID-19 vaccine regimen (anti-COVID-19 antibody negative or positive).

Estimates of the average antibody response and variance within and across cohorts will be obtained from a multivariate general linear regression model. Based on published data on the assays, it is anticipated that log-transformation of assay values will allow for Gaussian assumptions to hold, but alternative Box-Cox transformations of the data may be explored to stabilize the variance.

The primary and supportive analyses will also be replicated on the Per protocol population and using alternative strategies for missing data. Additional analysis details will be provided in subsequent versions of the SAP.

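### Titres below detection are set to LLOD/2 beside a Gaussian log-titre model with no method for left-censoring, so geometric means and between-arm differences will be distorted if many values fall below detection

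*SAP*

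**What the plan says.** SAP 8.2.1 sets the rule: "For concentrations that are below the Lower Limit of Detection (LLOD), numeric values equivalent to LLOD/2 are assigned before and for all descriptive reporting". SAP 8.2.4 summarises Week 4 titres by geometric mean, its CV and 95% CIs, along with the median and interquartile range. For the model, SAP 8.2.4 says "it is anticipated that log-transformation of assay values will allow for Gaussian assumptions to hold", with Box-Cox transformations as the alternative, and that the average response and variance "will be obtained from a multivariate general linear regression model". Protocol 13.4.4 adds that the logistic and linear models "will be used to compare response to additional homologous doses of COVID-19 vaccine for a variety of subgroups", including continue v withhold, vaccine type and class of immunosuppressant.

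Neither document names a censored-data method or a sensitivity analysis to the substituted value. The alternative strategies mentioned in SAP 8.2.4 are for missing data, and that section defers further detail to later SAP versions.

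On how often titres may be undetectable, Protocol 1.2.1 describes some patients who, "treated with mycophenolate and B cell depletion, have poor responses (8 U/ml and <0.4 U/ml, respectively". Protocol 13.7 says "those taking MMF or rituximab were at much higher risk of not mounting a detectable antibody response (89% and 67%, respectively".

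**The concern.** Every value below LLOD receives the same number. If there are many, the log titres have a spike at the floor, and neither a log nor a Box-Cox transform can make a spike Gaussian. The substituted values also hide how far below the floor an arm really lies. A low arm is therefore usually pulled up towards the floor, its SD is understated, and a true difference from a less censored arm is shrunk.

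The comparisons most exposed are those between arms with unequal shares below LLOD, such as class of immunosuppressant. The descriptive summaries are exposed too. If no protective threshold is available at a preliminary analysis, SAP 12 leaves only the descriptive titre summary, which is what the LLOD/2 rule governs directly.

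**Working it through.** **The plan's own figure.** No power or precision is stated for the titre analyses. The only comparable figure is the binary one in Protocol 13.7: 33 evaluable, at least 90% power for 0.50 against 0.25. It reproduces (reject at 13 or more of 33; exact alpha 0.0484, power 0.919) and does not depend on the LLOD rule.

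**Inputs.**
- Substituted value: LLOD/2, which is 0.301 below log10 LLOD (SAP 8.2.1).
- Participants: 40 per arm, the subgroup cap in Protocol 13.7.
- Log10 SD: assumed, 0.3 to 1.5.
- Share below LLOD at Week 4: assumed. Protocol 1.1 gives post-third-dose results only in transplant recipients: 44% of seronegatives became positive (56% did not), and titres rose in one third of antibody-negatives (two thirds did not). Multiplying by the undetectable rates in Protocol 13.7 gives, for rituximab, 0.67 × 0.56 = 38% to 0.67 × 2/3 = 45%. Using the 89% figure as well, the top of the range is 0.89 × 2/3 = 59%. Seronegative stands in for below LLOD here.

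**Formula.** Put log10 LLOD at 0, let log10 titre be normal with SD σ, let p be the share below LLOD and z its normal quantile. The true mean is −σz. After substitution the bias of the arm mean is

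σ[φ(z) + pz] − 0.301p.

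- p = 0.59: z = 0.2275, φ = 0.3887, bracket 0.5230, last term 0.1776. Bias 0.084 at σ = 0.5 and 0.345 at σ = 1.0.
- p = 0.38: z = −0.3055, φ = 0.3808, bracket 0.2647, last term 0.1144. Bias 0.018 and 0.150.

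**Geometric mean after substitution divided by the truth (10 to the power of the bias):**

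| Below LLOD | SD 0.3 | SD 0.5 | SD 1.0 | SD 1.5 |
|---|---|---|---|---|
| 38% | 0.92 | 1.04 | 1.41 | 1.92 |
| 50% | 0.93 | 1.12 | 1.77 | 2.80 |
| 59% | 0.95 | 1.21 | 2.22 | 4.04 |
| 67% | 0.99 | 1.34 | 2.85 | 6.08 |

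**Difference, 59% v 38%.** The true difference is σ(0.2275 + 0.3055) = 0.533σ.
- SD 0.5: true 0.267; substituted 0.267 − (0.084 − 0.018) = 0.201; retained 75%.
- SD 1.0: true 0.533 (3.4-fold); substituted 0.533 − (0.345 − 0.150) = 0.338 (2.2-fold); retained 63%.

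**Coverage of the nominal 95% CI, by simulation with 40 per arm.** For the difference: 90% to 91% at SD 0.5 and 74% to 77% at SD 1.0. For the mean of the arm with 59% below: 76% and 1%. With equal shares and equal SDs in both arms the difference is unbiased and coverage is 95%.

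**Left-censored normal (Tobit) fit, same scenario.** The estimate is close to the truth, with coverage of 94% to 95%. This is expected, because the data were generated to fit that model.

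**Tobit when its assumption fails.** Take 60% v 40% true non-responders placed 1 log10 below LLOD, and responders with means 1.5 and 2.0 above it (SD 0.5). The true difference is (−0.4 + 1.2) − (−0.6 + 0.6) = 0.80. Tobit gives about 1.0 (coverage about 94%). LLOD/2 gives about 0.65 (coverage about 92%).

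**The case against.** The strongest reply is that heavy censoring at Week 4 is not shown. The cited undetectable rates follow earlier vaccination, and the reference for 89% and 67% is titled as a single-dose study. The main titres are on the MSD assay, whose LLOD is not given; its positive threshold of 1,204.71 AU/mL is a different quantity. The caps also limit a filled arm: in Adult Stage 1 at most 40 of 60 can be at or below 50 U/mL before the dose, and in Adult Stage 2 and both pediatric stages at most 40 of 80 can be at or below 200 U/mL. All of this stands and makes the finding conditional. The subgroups at or below 200 and 50 U/mL could still have higher shares.

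The LLOD/2 rule is worded for descriptive reporting, so its use in the regression is inference. Medians and quartiles are already planned, and the seroconversion and logistic analyses do not use the substituted value. Secondary intervals are labelled descriptive in SAP 8.1.4. These points limit the consequence, but a descriptive label does not correct a biased geometric mean.

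Tobit is no cure-all: it extrapolates below LLOD from log-normality and can overshoot, as the non-responder example shows. That stands, and is why a rank-based check belongs beside it.

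Two stronger readings are tempting. A reader might infer that half or more of mycophenolate patients are undetectable. Protocol 13.7 gives 89%, but Protocol 1.2.1 gives 8 U/mL, which is detectable; the two need reconciling and cannot carry that claim. A reader might also infer that the linear-model contrasts are all that remains without a protective threshold. SAP 12 leaves only the descriptive titre summary, only at a preliminary analysis, and SAP 8.2.4 places the regression models in the final analysis.

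**Conclusion.** The gap is real: LLOD/2 is the only value defined for titres below detection, and the Gaussian log-scale summaries and model have no provision for left-censoring. The harm is conditional on a large share below LLOD and a log10 SD of about 0.5 or more. The case is best supported for cohorts C and F, from the 67% undetectable and the <0.4 U/mL quoted for B-cell depletion after earlier vaccination.

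The 59% v 38% illustration is not a forecast. Its upper share uses the disputed 89%, and both shares borrow from transplant recipients. At SD 0.3 the same scenario keeps 91% of the difference with about 95% coverage, and the geometric means are slightly understated.

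The documents do not support saying that the estimates are biased whatever the data show, or that the primary result is at risk.

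**What to change.** In SAP 8.2.4 and Protocol 13.4.3:
- Report the percentage below LLOD for each arm and visit, and state the LLOD of each assay.
- Fit the log-titre model as a left-censored (Tobit) regression with censoring at LLOD, with a rank-based comparison as a check on the assumption of log-normality below LLOD.
- Where more than about half of an arm is below LLOD, rely on the percentage below LLOD and the already planned median and quartiles, not the geometric mean.
- Keep LLOD/2 for plots and listings.

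The cost is SAP and protocol wording, a standard procedure and a little more analysis work, with no new data. The downside is a distributional assumption below LLOD that the data cannot fully test. The SAP already expects further versions, so the change can go into the next one.
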